**Consent for Qualitative Interviews****Caregiver:**

Consent procedures as previously described will be followed for those completing qualitative interviews. All who participate will provide verbal consent to be audiotaped (see 6.2 Protection Against Risks), which will be documented by the research assistant using a standardized form kept for documentation purposes. The qualitative researchers will not be blinded due to the purposes of the qualitative study and the type of data they are collecting.

**Providers and Staff:**

PCPs and staff members will be identified by clinic contacts for participation in qualitative interviews (one interview for each individual). The qualitative study RA will not interview more than one participant type from each clinic and sampling will be by convenience for this study component. Potential participants will be informed that a decline in participation will in no way impact employment and their employers will not know of their agreement or refusal to participate. Those who agree to participate will provide written consent, including consent to be audiotaped, which will be documented by the research assistant using a standardized form kept for documentation purposes (6.2 Protection Against Risks).

**E3. Subject Capacity**

If the caregiver, after following our standard consent procedures, demonstrates capacity using the below questions, verbal consent will be documented and the caregiver will be consented to the study. As far as patient consent is concerned, should the patient not demonstrate capacity to consent, but not refuse to participate, the RA/RC will follow the assent process and consent the caregiver. Consent covers participation in one survey and a qualitative interview. Once the consent process is completed, the RA will either complete the baseline interview or schedule a time for a follow-up phone call.

When obtaining consent we will use the standard procedures for addressing capacity that we have been used in many prior studies, but may modify this process to be in compliance with the IRB involved in this study as per their request. The following questions will be used:

*We have just reviewed what it means to participate in this study. I am going to ask you a few questions just to make sure you understand what we will be doing once we begin.*

1. *What would you be doing if you agree to take part in this study? (Examples of acceptable answers: "Take part in an interview/survey," or "Answer questions about my friend or relative.")*  
 Person is able to answer this       Person is not able to answer this
  
2. *What can you do or ask me to do if you are uncomfortable with a particular question in the survey? (Examples of acceptable answers: "Ask to skip the question." "Ask you to read another question.")*  
 Person is able to answer this       Person is not able to answer this

3. *What can you do if you decide after we start that you do not want to participate in the study? (Examples of acceptable answers: "Tell you that I do not want to answer any more questions.")*

Person is able to answer this     Person is not able to answer this

#### **E4. Subject/Representative Comprehension**

Potential subjects will be told that their involvement in the study is completely voluntary and that they can withdraw from the study at any point. Caregivers may themselves be elderly and might have cognitive impairment such that it impacts their capacity to consent to research. For all potential participants, we will assess the individual's ability to provide informed consent using IRB approved interview procedures to assess capacity to consent for research. Some subjects may be too hearing impaired to communicate by telephone and the telephone interview is designed to assess for this potential problem and mitigate this issue when possible but this might impair ones capacity to consent. Although we have conducted numerous studies with elderly subjects, this has been a rare occurrence. Nonetheless we will not enroll any caregiver participant who cannot communicate by telephone.

#### **E5. Documentation of Consent**

Those who agree to participate will provide verbal consent, including consent to be audiotaped, which will be documented by the research assistant in the REDCap library for clear documentation purposes. The providers that participate in the qualitative interviews will sign written informed consents and audio consent forms. These documents will be logged and kept in the study binder in a locked cabinet that is accessible only to the PI and the study coordinator.

#### **5.3 Study Specific Procedures**

Study procedures include caregiver surveys and interviews to evaluate the quality improvement program described in Section 4.

#### **5.4 Data Collection Overview (Evaluation)**

We will collect data from five sources:

- 1) Caregiver surveys
- 2) Caregiver qualitative interviews
- 3) Provider/Staff qualitative interviews
- 4) Patient data from Epic
- 5) Patient data from ResDAC (Research Data Assistance Center) claims data

1. **Caregiver surveys.** The survey will be administered over the telephone and participant responses will be entered in REDCap survey database. A blinded research assistant interviewer will collect complete telephone survey data from CGs at baseline, 6 months, 12 months and 24 months using a 30-minute survey (see Survey instrument). The RA will enter de-identified survey data from each survey wave into a HIPAA-compliant REDCap electronic database hosted at NYULH.
2. **Qualitative interviews** will be conducted with 40 dyads (or until thematic saturation is reached for key content areas) each from the INT and CON clinics. Caregiver Cognitive Interviews will also be conducted with an additional 20 caregivers to evaluate the use of

the Treatment Burden Questionnaire (TBQ) for Caregivers and identify any potential problems that may compromise the quality of data collected using the TBQ with caregivers. The purpose of these interviews is to validate this tool for future studies to measure treatment burden of caregivers. These 60 interviews will be audio recorded (included in verbal consent) and transcribed. Audio tapes will be destroyed once transcriptions are complete, which will be stored in a HIPAA-compliant NYU secure server.

3. **Provider/Staff Qualitative Interviews** will be conducted using purposive sampling framework with members from each category: internal medicine physician; specialty physician; care managements and nursing. Written informed consent will be obtained. Interviews will be conducting via phone. These interviews will be audio recorded and transcribed. Audio tapes will be destroyed once transcriptions are complete, which will be stored in a HIPAA-compliant NYU secure server.
4. **Patient data from Epic.** A trained member of the research team (Research Coordinator) who will be blinded to participant INT or CON group affiliation will be responsible for collecting and entering EHR data into REDCap for enrolled patients. The dyad will have consented verbally to review of their medical record in Epic. In order to evaluate this quality improvement intervention, the study team will pull and review administrative data from Epic on patients in the intervention and control clinics. These data will be de-identified and used to monitor safety and evaluate effectiveness of the intervention.
5. **ResDAC (Research Data Assistance Center) claims data** will be applied for in the 2nd or 3rd year of this study. An IRB modification will be submitted to obtain this data.

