## **5. Methods and Procedures (Evaluation)**

### **5.1 Screening and Identification**

We will use NYU Langone Health Epic to identify patients in the INT and CON clinics who meet inclusion and exclusion criteria listed in Section 3.2.

There will be three levels of screening:

- **Level 1:** Initial screening will be automated by settings in the EHR that generate a report based on inclusion criteria (above).
- **Level 2:** The initial list of patients generated by the EHR will be screened by the RA first through chart review for eligibility based on exclusion criteria (see Section 3.2). Should the patient not meet inclusion criteria, for example they don't actually have a diagnosis of diabetes, or speak English or Spanish; the patient will be removed from the list of potentially eligible patients.
- **Level 3:** Those patients who remain eligible following chart review to their PCP's in the INT clinics to notify them about their patients with DM-ADRD. The PCP's will be encouraged to review their list and decide if a patient is misclassified or inappropriate; some will review the lists and some will not. Any patient a PCP indicates as inappropriate or misclassified will be ineligible and will be screen failures. The amended list of eligible patients with both DM and ADRD for both the INT and CON clinics will go back to the RM who will send a letter to the patients informing the patients/caregiver of the quality improvement program and of a potential telephonic survey.

While eligible patients are easily identified by Epic, their caregivers (the respondents to the surveys and interviews to evaluate the quality improvement program) are not always listed in the patient chart. To identify an appropriate caregiver, a letter from the primary care physician will ask the patient to read the letter and then give it to their caregiver. The letter will explain the quality program briefly and state that a research assistant will call the patient's home unless they do not want to be called.

If the dyad, for whatever reason, does not want to participate in a call, they will be asked to opt out using the Standard Operating Procedure (SOP) of NYU Langone Health as outlined in SOP #HSR-312, Version Number 2.0. This SOP states that patients are able to opt-out of the Direct Recruitment process either by [contact]) or email ([contact]). Patients who wish to opt out must provide at least three of the following identifiers:

1. Full name
2. Date of birth
3. Address

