### ***Step by step process of consent:***

1. **INT:** RA mails letter (see Patient Letter) to patients in INT clinic signed by the clinic director, lead physician, or primary provider (depending on clinic preference) informing them about EQUIPED quality improvement program and evaluation.
2. **INT and CON:** RA calls eligible patient and/or caregiver using contact information from patient chart in EHR. If caregiver information is not available in the chart, the RA will ask the patient for caregiver contact information.
3. **INT and CON:** RA screen Patient and/or Caregiver for Capacity to Consent (See section E3)
  - a. If the patient demonstrates capacity, the patient is deemed able to provide verbal consent to have the study team talk to the caregiver to obtain their verbal consent

and to have the study personal obtain and analyze health data (medical records and claims).

- b. If the patient does not have capacity and assents to the study, the RA is able to speak to the caregiver who provides verbal consent for the caregiver survey , and the Health Care Proxy (HCP) (who may or may not be the caregiver) provides verbal consent for study personnel to obtain and analyze the patients' health data (medical records and claims).
- c. If the patient does not have capacity, and refuses (no assent), the dyad will not be enrolled although the clinical team (Panel Manager) can re-contact that dyad over time to offer improved care quality.

4. **INT and CON:** If the caregiver demonstrates capacity (screened using Capacity to Consent, at the discretion of the RA) verbal consent will be documented by the RA in REDCap and the caregiver will be consented to participate in the study. Caregiver consent covers participation in 4 telephone surveys.

A healthcare proxy is an individual who is designated as a representative/agent through a health care proxy signed by both the subject and the appointed representative/agent. For a health care proxy to be effective, it must have been signed at a time when the subject had decision-making capacity. In addition, the health care proxy must not specifically prohibit research. Determination of the legal authority of a surrogate will be obtained through Epic, or verbally by the patient and/or caregiver.

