Consistent PCP care	EHR	% Visits by PCP versus other ambulatory providers	Pt	X	X	X	X

New home health aide or increased hours	Survey	Yes/no; HHA resource changes	Pt	X	X	X	X
New home health care services	Survey	Yes/no	Pt	X	X	X	X
Insurance	EHR	Categorical: Yes/No, Medicare, Medicaid, HMO	Pt	X	X	X	X
DM-ADRD-Specific							
Has a caregiver (Defined: Sec. B5)	EHR	Yes/No	Pt	X	X	X	X
Caregiver living arrangement	Survey	Categorical: Live with subject, close proximity (miles), other	CG	X	X	X	X
Clinic-Specific							
Clinic Size	Admin	Number primary care providers / number of patients	Clinic	X			X
Clinic Support	Admin	Number of clinic support staff / provider	Clinic	X			X
Proportion Medicare/Medicaid	Admin	Insurance data specific to Medicare/Medicaid categories	Clinic	X			X
EQUIPED Process of Care Measures							
Provider use of structured template	EHR	Counts: visit note/templates; proportion of visits with templates	PCP		X	X	X

Provider educational attendance	Admin	Proportion (n, %) of educational sessions attended	PCP		X		
PM – PCP Communication	EHR	Counts: emails, forwarded notes between PM and PCP	PM/PCP		X	X	X
Change in diabetic medication	EHR	Counts: change (add, delete); dosing (increase, decrease)	Pt	X	X	X	X
Change in antihypertensive medication	EHR	Counts: change (add, delete); dosing (increase, decrease)	Pt	X	X	X	X
Medication complexity	EHR	Sum of unique medications, daily dosing frequency/differences	Pt	X	X	X	X
Anticholinergic medication burden	EHR	Anticholinergic medication burden scale	Pt	X	X	X	X
PM – CG contact frequency	EHR	Counts: CG visits with PM (by type: email, phone, in-person)	CG		X	X	X
Referrals for CG-support services	EHR	Proportion (n, %) of CGs referred to programs / receipt of service	CG		X	X	X
Cognitive screening of eligible patients	EHR	Proportion (n, %) of DM-eligible patients screened w/ MiniCog TM39	Pt		X	X	X
Outcome Measures							
General							
Hemoglobin A1C Change	EHR	Proportional change: patients with in-range values versus not	Pt	X	X	X	X

Blood pressure change	EHR	Proportional change: patients with in-range values versus not	Pt	X	X	X	X
Treatment Burden Questionnaire	Survey	15-item survey modified for CG administration (0-10 likert) 	Pt	X	X	X	X
Non-acute care use	ResDAC	Counts: provider ambulatory visits / all health system contacts	Pt	X	X	X	X
Acute care use**	ResDAC	Counts: ED, hospital / #bed days	Pt	X	X	X	X

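### Section 5.4 calls the survey RA and the EHR abstractor blinded, but the plan's procedures do not secure this, and no rule fixes which HbA1c or BP reading counts

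*Combined protocol and SAP*

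**What the plan says.** Section 5.4 (Data Collection Overview) makes two claims of blinding.

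- EHR data: a Research Coordinator "who will be blinded to participant INT or CON group affiliation will be responsible for collecting and entering EHR data into REDCap".
- Caregiver surveys: "A blinded research assistant interviewer will collect complete telephone survey data from CGs at baseline, 6 months, 12 months and 24 months".

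Other sections describe what these roles do and what the chart contains.

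- Table 1 lists two process measures with the EHR as source, at 6, 12 and 24 months: panel manager (PM) to PCP communication, "Counts: emails, forwarded notes between PM and PCP", and PM to caregiver contact, "Counts: CG visits with PM (by type: email, phone, in-person".
- Section 4 describes PMs under INT clinics only, and says that PCPs receive PM information through notes and in-basket messages in Epic.
- The consent steps in Section 5.2.1 begin with an item marked INT: "RA mails letter (see Patient Letter) to patients in INT clinic". The RA then telephones patients or caregivers in both arms, using contact details from the chart.
- E3 (Subject Capacity) says that after consent "the RA will either complete the baseline interview or schedule a time for a follow-up phone call".
- Section 5.1 has the RA review charts for eligibility. It then says that the list of eligible patients for both arms "will go back to the RM who will send a letter to the patients".

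The Measures text says that HbA1c and BP come from the EHR at 0, 6, 12 and 24 months if a value is available. It gives no window around these times and no rule for several readings.

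**The concern.** Blinding of assessors is a stated property of this trial, and readers of the results will rely on it. Neither PCPs nor caregivers are said to be blinded, so the interviewer and the abstractor are the only masking the quantitative evaluation has. If either learns the arm in the ordinary course of the work, the report would claim a protection that was not there.

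Two groups of outcomes are exposed. The first is in-range HbA1c (the primary outcome in Section 7) and in-range BP (named in the second specific aim). Each is objective once a reading has been fixed, but the plan does not fix the reading. The second is the caregiver-reported scales collected by telephone, such as the Treatment Burden Questionnaire and the dementia severity scale, where the manner of asking and recording can matter.

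**Working it through.** The documents give no figure on this point, so there is nothing to reproduce. The check compares each blinding claim with the procedures around it.

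**1. The Research Coordinator.**

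- Claim: blinded while collecting and entering EHR data (Section 5.4, item 4).
- Contact and message counts for a PM can be non-zero only where there is a PM, that is, in INT clinics (Section 4). Whoever collects these two EHR items sees the arm.
- PM notes are in Epic. A person who opens an INT patient's chart for another reason, such as medication changes or BP, may come across them.
- Randomization is by practice (Sections 1.2 and 3.1). A chart that shows the clinic gives the arm to anyone who knows the allocation of clinics.
- No section assigns the PM items to a different person, extracts them later, or hides notes and clinic from the abstractor.

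The claim is therefore unsupported. The text stops short of proving that it is false, because it does not say that the Coordinator personally extracts the PM items. The Measures text says that process measures come partly from EHR review and partly from Epic administrative systems, and does not give the split.

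**2. The survey RA at baseline.**

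- Claim: blinded at all four survey waves, baseline included (Section 5.4, item 1).
- Section 5.2.1, step 1: the RA sends a letter in INT. No matching CON step is listed.
- Section 5.2.1, step 2: the RA calls both arms from the chart.
- E3: the RA completes the baseline interview, or schedules it, once consent is done.

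Read in sequence, one role performs an INT-only act and then conducts the baseline survey. Section 5.1 conflicts with this on who mails (RM rather than RA) and to whom (a list covering both arms). RM is not defined in the list of abbreviations, so it may be a separate role or a slip for RA.

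Settling that conflict in favour of the RM would not by itself blind the RA. Section 5.1 also gives the RA chart review, and the calls are made from the chart, so the clinic can still be seen.

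**3. The survey RA at 6, 12 and 24 months.**

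The text does not say whether the same RA makes the follow-up calls. It describes no separate interviewer and no script asking caregivers not to mention the PM. INT caregivers will have been in telephone contact with the PM, so some may mention it. Unblinding at follow-up is likely, but it is an inference.

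**4. The consequence for HbA1c and BP.**

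For knowledge of the arm to bias in-range status, two conditions are needed: a person who knows the arm, and discretion over the reading. Points 1 and 2 show that the first is not excluded. The second arises because there is neither a window nor a rule for several readings. Discretion then covers which reading is used and whether a time point counts as missing.

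It operates only if the values are taken by hand. Section 5.4, item 4 describes manual collection and entry by the Coordinator and also an administrative pull from Epic, and does not say which supplies HbA1c and BP.

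The exposure is larger for BP, which a chart may record many times. HbA1c is a laboratory result, so bias can enter only through which result is chosen or treated as missing.

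**5. Size.**

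An estimate would need the share of patients with both an in-range and an out-of-range reading in the window, and how often the choice between them would depend on the arm. The documents give neither figure, nor the window itself. Any number would be an invention, so none is offered.

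**The case against.** The strongest reply is that no biased step is documented. The primary outcome is a recorded laboratory value that interviewers never touch. The administrative pull from Epic may supply HbA1c and BP without anyone choosing a reading, and Section 6.2 names data-management staff who handle the administrative data and the combined database. The two PM items have PM/PCP and caregiver, not patient, as their subject in Table 1, so they may lie outside the Coordinator's task, which is headed patient data. The RA overlap concerns recruitment and baseline, before arm differences are assessed. The missing reading rule is a gap in the endpoint definition with or without blinding.

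Much of this stands, and it limits the point. A reader might infer that an arm-aware person picks BP and HbA1c readings from the chart by hand; the documents do not say so, because the route is left open. A reader might also infer that all follow-up interviews are unblinded; nothing says that the same RA conducts them. Qualitative interviewers are openly declared unblinded in Section 5.2.1 and are not part of any contradiction.

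The reply does not restore the two claims. It relies on a division of work that the plan never states. That the reading rule is missing for other reasons too does not help: it is what would allow knowledge of the arm to matter.

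**Conclusion.** The point holds as a gap between stated blinding and described procedure. For the Research Coordinator, blinding is claimed over a source that includes INT-only content, with no separation from the outcome data. For the RA, the claim at baseline conflicts with the consent steps, and those steps conflict with Section 5.1 on the mailing. At 6, 12 and 24 months the loss of blinding is likely but not stated.

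For HbA1c and BP the conclusion is conditional. If readings are abstracted by hand, someone aware of the arm could influence which one sets in-range status, with more room for BP than for HbA1c. If they come from an automated pull with a fixed rule, that path is closed. The size of any bias cannot be estimated from the documents. The conclusion rests on PMs working only in INT clinics, as Section 4 describes, and on no unpublished procedure dividing the tasks.

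**What to change.** 1. Extract HbA1c and BP for both arms by one automated Epic query, with a pre-specified window around each time point and a fixed rule for several readings. State in Section 5.4 that this is the route.
2. Lock that file before any PM process field is extracted.
3. Reconcile Sections 5.1 and 5.2.1 on who mails the letter and to which arm, and define RM.
4. In Section 5.4, remove or qualify the word blinded wherever the procedures cannot support it, including for an RA who sees the clinic through chart review or calls made from the chart. Reassigning the mailing is not enough to keep the claim.

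The cost is a small amount of Epic report programming, some protocol wording, and a less favourable blinding statement. These four steps need no extra staff. If the team wants to keep a claim of blinded follow-up surveys, it would also have to separate recruiting RAs from follow-up interviewers and add a script asking caregivers not to mention the PM. That is optional and may affect staffing.

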## 5.2 Consent Procedures and Documentation

### 5.2.1 Process of Consent

The patient and caregiver (dyad) is enrolled in the study (the evaluation of the RCT of a quality

improvement program) when verbal consent (or assent, see E3) is obtained from the patient and caregiver.

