We will also measure structure of care variables. These include patient use of consistent PCP care, home health services, and patient insurance. Clinic characteristics are size, support staff number, proportion of Medicare and Medicaid patients. Several baseline variables relate to diabetes but because they are also outcome variables they will be described later. As shown in table 1, many of these baseline and control variables are measured in the EHR and Epic administrative reports, or by claims. Some are measured by validated survey instruments, which are discussed briefly below.

We will collect many process of care measures at baseline and at follow-up. These include: a) provider use of Epic templates and tools; b) provider attendance at educational sessions; c) PM-PCP communication; d) PM-caregiver contact frequency; e) referral for caregiver-support services; f) cognitive screening of diabetes patients over 75; g) change in diabetes medications; h) change in hypertensive medications; i) change in anticholinergic burden; j) change in medication complexity. These variables are measured by EHR review and Epic administrative systems.

Outcome variables include HbA1c level and blood pressure. These variables will be measured at 0, 6, 12 and 24 months when available. Our main outcome is the proportion of patients achieving consensus HbA1c targets. BP will be measured by proportion of patients achieving consensus BP targets per our guideline. These variables will be measured by the EHR.

Utilization outcome variables are ED, hospital, SNF and ambulatory clinic utilization measured by EHR and by claims (for non-New York Langone Health utilization). SNF days must be measured by claims; Epic reports have discharge destination but do not have SNF days. Utilization variables will be measured at 6, 12, 24 months; the baseline measures include a 20 month look back at utilization.

Multiple caregiver reported outcomes about the caregiver and about the patients will also be

collected at 0, 6, 12, 24 months. General outcomes include: a) caregiver perception of care quality (our main caregiver-reported outcome), dyad care goals, preferences, and satisfaction; b) treatment burden; c) caregiver global health. Dementia and diabetes specific outcomes include: a) patient dementia symptoms; b) caregiver diabetes stress.

Below is a brief description of the instruments we will use, all of which have been studied and validated, although not always with caregivers.

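### The EHR-measured HbA1c outcome appears to rest on dyads enrolled after allocation through arm-specific steps, and Section 7 has no analysis that addresses the selection this may cause

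*Combined protocol and SAP*

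**What the plan says.** **Outcome and source.** The Measures section states: "Our main outcome is the proportion of patients achieving consensus HbA1c targets". Of HbA1c and BP it says: "These variables will be measured by the EHR". Both are scheduled at months 0, 6, 12 and 24, when available.

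**Whose records.** Section 5.4, item 4, makes a research coordinator "responsible for collecting and entering EHR data into REDCap for enrolled patients", and adds: "The dyad will have consented verbally to review of their medical record in Epic". Under Section 5.2.1 a dyad is enrolled "when verbal consent (or assent, see E3) is obtained from the patient and caregiver". If the patient lacks capacity, the consent steps also require a health care proxy, "who may or may not be the caregiver) provides verbal consent for study personnel to obtain and analyze" the patient's health data. A patient who refuses is not enrolled.

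**The second data source.** The same item continues: "the study team will pull and review administrative data from Epic on patients in the intervention and control clinics". These data are to be de-identified and used for safety monitoring and for evaluating effectiveness. The item says neither all patients nor enrolled patients only, and does not mention HbA1c.

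**Steps that differ by arm.**
- Section 5.1, Level 3, sends lists to PCPs in INT clinics. Patients whom a PCP marks as unsuitable become screen failures. Section 4 gives CON providers an initial list too, but describes no such review of it.
- In INT, the panel manager approaches patients aged 75 or over with HbA1c or BP out of range for cognitive screening, and those who screen positive join the program. In CON, screening is only encouraged.
- The consent steps give the mailed letter for INT only, whereas Section 5.1 implies letters in both arms.

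**Analysis.** Section 7 gives a logistic mixed model with practice as a random effect. It defines no analysis population. Its sensitivity analyses deal with missing outcome values among participants.

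**The concern.** Randomising clinics makes the clinics' eligible populations comparable. It does not do so for patients recruited later by procedures that depend on the arm. Section 7 relies on randomisation to make further covariate adjustment largely unnecessary. That argument does not carry over to a set formed after allocation.

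If the chance of being identified, kept on the list, reached and consented depends on glycaemic control, and does so differently in INT and CON, the HbA1c and BP contrasts mix the program's effect with a difference in who was enrolled. The missing-data analyses cannot detect this, because people who were never enrolled have no record in the analysis set. Records that might show the problem could fall within the Epic pull in Section 5.4, but the plan does not say so and specifies no analysis of that pull.

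**Working it through.** **1. Must the sample include patients identified after allocation?** Section 4 expects 20 to 50 diagnosed patients per INT clinic and has 9 INT clinics: 9 × 20 = 180 and 9 × 50 = 450. The goal is 500 per arm. Even full consent from the diagnosed list falls short, so INT needs patients found by screening, referral or refreshment. The same holds in CON only if its clinics are of similar size, which is an assumption. On the plan's other figure, 2 panel managers × 300 dyads = 600, and 500/600 = 83% would have to enrol.

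**2. Selection through enrolment, no true effect.** The documents give no on-target rate, enrolment rate or ICC. Assume 50% on target at baseline, and CON enrolment unrelated to control. Let c1 and c0 be the INT enrolment rates of on-target and off-target patients. The on-target share among enrolled INT patients is

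p* = 0.5·c1 / (0.5·c1 + 0.5·c0), with an induced odds ratio of c1/c0.

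This is the gap if selection acts on the analysed status itself. Enrolment comes before follow-up, so the gap at follow-up is smaller. If 80% of baseline on-target and 20% of off-target patients are later on target (assumed), the gap is multiplied by 0.8 − 0.2 = 0.6.

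| INT enrolment, on / off target | p* | Gap at baseline | Gap at follow-up (× 0.6) |
|---|---|---|---|
| 65% / 60% | 0.520 | +2.0 points | +1.2 points |
| 65% / 55% | 0.542 | +4.2 points | +2.5 points |
| 70% / 50% | 0.583 | +8.3 points | +5.0 points |

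If c1/c0 is the same in both arms, the gap is zero.

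**3. False-positive rate at two-sided 0.05.** Take 500 per arm and 9 clinics per arm, so m = 500/9 = 55.6. The design effect is 1 + (m − 1)·ICC and the effective n per arm is 500/DE: 500 at ICC 0, 323.5 at 0.01 and 134.1 at 0.05. With z = gap / √[p*(1 − p*)/n + 0.25/n], where p* is the INT proportion in the column used, the rate is 1 − Φ(1.96 − z) + Φ(−1.96 − z).

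| INT enrolment | Baseline gap, ICC 0 / 0.01 / 0.05 | Follow-up gap, ICC 0 / 0.01 / 0.05 |
|---|---|---|
| 65% / 60% | 9.7% / 8.0% / 6.2% | 6.7% / 6.1% / 5.4% |
| 65% / 55% | 26% / 19% / 10.5% | 12.4% / 9.8% / 6.9% |
| 70% / 50% | 76% / 57% / 28% | 35% / 25% / 13% |

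**4. Selection through case finding can act the other way.** Section 4 expects screen-positive patients to be about as numerous as diagnosed ones, so let half of INT be screen-found. Assume 55% of diagnosed and 35% of screen-found patients are on target. INT is then 0.5 × 0.35 + 0.5 × 0.55 = 45%. If a quarter of CON is screen-found, CON is 0.25 × 0.35 + 0.75 × 0.55 = 50%, a gap of −5 points. If none is, CON is 55%, a gap of −10 points. The sign of the net bias is therefore not known in advance.

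**The case against.** **The bias is not inevitable.** With no true effect, it needs enrolment to depend on control differently by arm. Consent is to the evaluation rather than to care: the clinical team may still offer the program to dyads that do not enrol, and survey payments do not differ by arm. This stands, and the point is one of risk. It does not remove the arm-specific list review and case finding, which act before consent.

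**Baseline HbA1c can be used.** Status at month 0 comes from the EHR, and Section 7 will consider adjusting for factors that look unbalanced. A reader might infer that no covariate can repair the problem. That goes too far: conditioning on baseline on-target status removes selection that works only through that status. Selection on unmeasured factors would remain. At present the adjustment is conditional and does not name baseline HbA1c.

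**The wider data may not exist for this purpose.** A reader might infer that Epic data on every eligible patient are already being pulled, so that the selection is plainly avoidable. Section 5.4 does not settle this. If the pull covers everyone, it may already be meant for the effectiveness analysis. If it covers enrolled patients only, there is nothing wider to use. The waiver requested in Section 5.2 is tied to obtaining verbal consent, so access to non-enrolled patients' records cannot be assumed.

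**An EHR list is a different population.** It contains misclassified patients whom chart review would remove, it cannot reliably apply the caregiver criterion because caregivers are not always in the chart, and it omits patients found later. This stands, and it is why the list suits a supporting analysis rather than a replacement.

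**Conclusion.** The concern holds as a gap in specification and a risk of bias. The documents establish an EHR-measured primary outcome, EHR entry for enrolled and consenting dyads, recruitment after allocation through steps that differ by arm, and no analysis in Section 7 of non-enrolment or of the Epic pull.

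They do not establish that the HbA1c result is biased, in which direction, or that wider data are already in hand. Under the assumptions above, selection through enrolment in INT alone gives about +1 to +8 points, toward the lower end once partial persistence is allowed for. Unequal case finding gives −5 to −10 points in the example shown. For scale, with 50% on target in controls, 500 per arm and 9 clinics per arm, the difference detectable at 80% power is 8.9 points at ICC 0 and 16.8 at ICC 0.05. These are illustrations, not estimates.

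A reader might also infer that a benefit seen in enrolled patients but not in the full list must be due to selection. That does not follow: dilution, different case mix or lower precision could each produce the same pattern.

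**What to change.** 1. State in Section 7 which Epic dataset and which patients form the primary HbA1c analysis, and state in Section 5.4 whether the administrative pull includes non-enrolled patients and contains HbA1c and BP.
2. Subject to IRB confirmation, add a supporting analysis of HbA1c and BP with the same mixed model in all patients on the automated Level 1 eligibility list of INT and CON clinics. Fix the list at one common date for both arms, at or before allocation and before PCP review, case finding or consent. A clinic-specific start date would not serve, because staggered panel-manager entry is defined for INT only.
3. In both sets, adjust for baseline on-target status as a pre-specified covariate.
4. Report enrolment rates by arm and baseline HbA1c status.
5. State in advance that a difference between the two sets may reflect selection, dilution, case mix or lower precision.

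**Cost.** Additional SAP text, one further model run per outcome and an enrolment table. Use of non-enrolled patients' records may need IRB approval and possibly a protocol amendment. The supporting estimate will be diluted by patients the panel manager never reached and by some misclassified patients. If the IRB declines, items 1, 3 and 5 can still be done for the enrolled set, with item 5 reduced to a stated limitation. Item 4 then depends on whether baseline HbA1c for non-enrolled patients may be tabulated in aggregate.
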